8.3.4 Exploratory Endpoints

Exploratory endpoints are:

- Outcome Measures in Rheumatology – Osteoarthritis Research Society International (OMERACT-OARSI) responder rate (1) at 2 years
- PGIC over 2 years
- Changes from baseline in the scores of the KOOS QOL and the MOS SF-36 questionnaire over 2 years
- Change from baseline in KOOS Symptom Index over 2 years
- Change from baseline in pain score in the target and contralateral knee over 2 years using an 11-point NRS
- Change from baseline in presence of pain in other joints over 2 years
- Change from baseline in ICOAP scores over 2 years

- Change over time in structural as well as compositional parameters of the knee joint (e.g., synovium, menisci, bone, and other structures) as evaluated by MRI
- Change from baseline in serum, urine, and synovial markers associated with administration of the compound
- Baseline protein markers and/or genetic markers associated with response to treatment or disease progression (response assessed by MRI and/or questionnaire)
- Changes in MRI outcomes, WOMAC scores, 20-meter walk test, PGA, PGIC, JSW, OMERACT-OARSI responder rate, KOOS QOL, KOOS Symptom Index, MOS SF-36, NRS pain score in the target and contralateral knee, presence of pain in other joints, ICOAP, safety laboratory values, and vital signs over the extended follow-up period and nature, incidence and severity of local and systemic AEs during the extended follow-up period (to be summarized descriptively)
- Relationship between dosing (dose and regimen), cartilage structure, and clinical scores as a function of time

The Outcome Measures in Rheumatology – Osteoarthritis Research Society International (OMERACT-OARSI) responder rate (1) will be determined as an exploratory analysis. The OMERACT-OARSI responder criteria involve changes that are deemed to be clinically relevant in three domains: pain, function, and Patient’s Global Assessment. For each of these domains, ranges are defined for absolute and percent changes from baseline that correspond to “high improvement” and “moderate improvement”. OMERACT-OARSI response is defined as either i) high improvement in pain or function or ii) moderate improvement in at least 2 of the 3 domains (pain, function, and Patient’s Global Assessment).

In this trial, OMERACT-OARSI response will be determined using WOMAC pain and function index scores and the PGA described in Section 7.3.3.

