- 3. baseline mal-alignment in target knee (< -3 or > 3 or [-3,3] degrees)

Pain medications [classified for 3 timing groups defined in Section 14]:

- 1. Pain medications (Yes, No) any of 2, 3 or 4 defined below
- 2. Analgesics, Opiods in WHO ATC code group N02A (Yes, No)
- 3. Analgesics, Other analgesics and antipyretics in WHO ATC code group N02B (Yes, No)
- 4. Non-steroid anti-inflammatory and antirheumatic products in WHO ATC code group M01A (Yes, No)

Other subgroups:

Subgroups defined by SNPs and biochemical biomarkers cutoffs subgroups (see Section 16.4);

A listing of protocol-permitted concomitant pain medications and their respective washout times was provided in Appendix 19.2. Prior to unblinding this list may be updated.

Subgroups will be defined by individual listing prior to database lock and prior to breaking the blind for the reporting of the treatment phase.

11 General Specifications for Statistical Analyses

It is planned to perform the statistical analysis in two steps. Approximately one month after the last subject reaches day 819 of the 2-year DBPC treatment phase, the database will be partially locked, the treatment code will be un-blinded. Thereafter, complete analyses will be performed, and a detailed CTR will be written based on the data collected up to the end of the DBPC treatment phase (day 819). Long term follow-up data (from Year 2 to Year 5) will be integrated and analyzed with the DBPC treatment phase data but reported separately from the DBPC treatment phase results. Investigators, other site staff, study monitors, and subjects will remain blinded to study treatment during the extended follow-up phase as described in Section 8. X-ray and MRI readers will remain blinded to study treatment until completion of the extended follow-up phase results.

A list of endpoints according to treatment phase is provided in Appendix 19.1.

Summary Statistics

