16.2 Secondary Efficacy Endpoint Analyses

Secondary endpoints related to structure:

Cartilage thickness

Cartilage thickness in the medial and lateral compartments will be summarised per timepoint (including LOCF) along with absolute and relative change from baseline. These will be calculated in two ways corresponding to the calculation of cartilage Average and Total thickness:

- 1. Medial
 - a. MFTC.VC/(cMF.tAB+MT.tAB), primary
 - b. MFTC ThCtAB aMe
- 2. Lateral:
 - a. LFTC.VC/(cLF.tAB+LT.tAB), primary
 - b. LFTC ThCtAB aMe

All these variables will be included in the ADAM. Only (1a) and (2a) will be used in summaries and analyses, the others (1b) and (2b) will only be derived in ADaM.

The absolute change from baseline in the medial and lateral compartments over 2 years will be analysed using a similar ANOVA model as the model used for the primary endpoint. Similarly to the analysis of the primary end-point, sensitivity analyses on ranked data will also be performed.

Cartilage Volume

Cartilage volume in the medial and lateral compartments as well as in the total femorotibial joint will be summarised per timepoint (including LOCF) along with absolute and relative change from baseline. These will be calculated as MFTC.VC, LFTC.VC, and MFTC.VC + LFTC.VC respectively.

The absolute change from baseline over 2 years will be analysed using a similar ANOVA model as the model used for the primary endpoint.

Joint Space Width

Minimal JSW (mJSW) in the medial and lateral compartments will be summarised per timepoint (including LOCF) as well as absolute and relative change from baseline for target knee as well as for contralateral knee.

The absolute change from baseline over 2 years will be analysed using an ANOVA model similar to the primary endpoint for target knee only.

Secondary endpoints related to function and symptoms:

WOMAC Total Score

WOMAC total scores (and WOMAC sub scores, as described below) will be displayed descriptively after being transformed to a scale of 0 to 100 using the formula described below.

All items have 11 possible answers ranging from 0 (no problems) to 10 (extreme problems). Given items I1 to Ix as the answers to each questionnaire item on a given subscale and the raw score as the *arithmetic mean* of the respective non-missing answers of items I1 to Ix, the subscale summary score will be calculated as:

$$\left[\frac{(mean\ score\ of\ subscale)}{10}\right]\cdot 100$$

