The WOMAC total score, and absolute changes from baseline in the WOMAC total score for the target knee will be presented with summary statistics for all timepoints (including baseline, post-treatment, and LOCF).

Absolute change from baseline in WOMAC total score over 2 years will be considered a continuous variable and will be analysed using a model similar to the ANOVA model used for the primary endpoint.

If an entire questionnaire is missing for a time point, no imputations will be performed for that time point. If some items are missing, imputation for Total score (and for sub scores) will be performed using same principal used for KOOS.

WOMAC Sub Scores

WOMAC sub scores (weight-bearing pain score (sum of items: walking, going up and down stairs, and standing), pain, function and stiffness) will be tabulated descriptively as described above for Total score.

Absolute change from baseline in pain, function, stiffness, and weight-bearing pain, over 2 years will be analysed using a model similar to the ANOVA model described under primary endpoint.

WALK test

Time needed to complete the 20-meter walk tests as well as absolute change from baseline will be presented with summary statistics per timepoint (including LOCF). No imputation for missing data will be done. Absolute change from baseline in time needed to complete the 20-meter walk will be analysed using a model similar to the ANOVA model described under primary endpoint.

Patient Global Assessment (PGA)

The Patient Global Assessment is based on subject's answer to the question "Considering all the ways your osteoarthritis of the knee has affected you during the last 48 Hours, select the number that best describes the impact of your knee osteoarthritis on your daily life", and can take on values between 0-10 (0=None, 10=Extreme), for summaries the values are rescaled to 0-100 by multiplication with 10.

The Patient Global Assessment will be presented with summary statistics per timepoint (including LOCF) as well as absolute change from baseline. Mean score will be presented as described for continuous variables, and also number and percentages per score will be presented. No imputation for missing data will be done (except LOCF).

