16.5 Other Endpoint Analyses

Outcome Measures in Rheumatology

Based on the assessments of WOMAC pain subscore, WOMAC function subscore, and PGA, ranges are defined for absolute and percent changes from baseline that correspond to "high improvement" and "moderate improvement".

OMERACT-OARSI response is defined [9] as either

- i) high improvement (relative change \leq -50% and absolute change \leq -20) in WOMAC pain or WOMAC function or
- ii) moderate improvement (relative change \leq -20% and absolute change \leq 10) in at least 2 of the 3 domains (WOMAC pain score, WOMAC function score, and PGA score).

Responder rate per domain will be summarized per treatment and analysis time point (including LOCF) along with absolute and percentage change-from-baseline in WOMAC pain, WOMAC function, and PGA score.

No imputation for missing data will be done.

Responder analyses for 2 years will be analysed using Logistic regression (SAS Proc Genmod), for outcomes response, high improvement, and moderate improvement. Treatment and pooled country will be included in the model:

```
proc genmod data=qs2 desc;

class grpn CNTRGR1N;

model aval = grpn CNTRGR1N / dist = bin link = logit type3;

estimate '30µg x2 vs Placebo' grpn -1 1 0 0 0 / exp;

estimate '30µg x4 vs Placebo' grpn -1 0 1 0 0 / exp;

estimate '100µg x2 vs Placebo' grpn -1 0 0 1 0 / exp;
```

```
estimate '100\mug x4 vs Placebo' grpn -1 0 0 0 1 / exp ; run ;
```

This analysis will be performed only if more than 10% of all subjects in the ITT analysis set satisfy condition i) or ii) above.

Patient Global Impression of Change (PGIC)

The PGIC score is based on subject's answer to the question: "Since getting the first injection of study treatment in your knee how would you describe the change in overall symptoms for this knee" and can take on values between 'Very much improved' 'Very much Worse' with 7 possible choices. The PGIC will be summarised by treatment and analysis timepoint (including LOCF). No imputation for missing data will be done.

Knee Outcome in Osteoarthritis Score (KOOS)

In this study the following two knee-related subscales of the KOOS are collected:

- Symptoms (items S1 to S5);
- Quality of life (items Q1 to Q4).

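### As printed, the absolute-change condition for OMERACT-OARSI moderate improvement excludes nobody, so the rule is percent-only (minor; check the sign at source)

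*SAP*

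**What the plan says.** SAP 16.5 gives two routes to response. The first is "high improvement (relative change \leq -50% and absolute change \leq -20) in WOMAC pain or WOMAC function or" the second, which is "moderate improvement (relative change \leq -20% and absolute change \leq 10) in at least 2 of the 3 domains". The three domains are WOMAC pain, WOMAC function and PGA.

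Protocol 8.3.4 prints no cut-offs but requires both kinds of change: "For each of these domains, ranges are defined for absolute and percent changes from baseline that correspond to" high and moderate improvement. SAP 16.5 opens with the same two-part idea, and SAP section 9 declares no departure from it.

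SAP 16.2 fixes the direction of the scales. For WOMAC: "All items have 11 possible answers ranging from 0 (no problems) to 10 (extreme problems", with sub scores then put on 0-100. PGA "can take on values between 0-10 (0=None, 10=Extreme), for summaries the values are rescaled to 0-100 by multiplication with 10". Later in SAP 16.5, the separate WOMAC responder is a decrease of at least 10 points on 0-100.

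The moderate rule feeds several outputs:
- per-domain responder summaries at each time point;
- logistic regression "for outcomes response, high improvement, and moderate improvement";
- the condition for running that regression: "This analysis will be performed only if more than 10% of all subjects in the ITT analysis set satisfy condition i) or ii) above".

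**The concern.** The two routes are built in parallel, yet one absolute limit is negative and the other positive. Where improvement is a fall in score, an upper limit of +10 on the change would admit even some worsening. Paired with a 20% fall, it can never bind. A program written literally from this text would classify moderate responders on percent change alone. A subject with a low baseline could then qualify on a fall of only a few points. At stake are the reported levels of moderate, per-domain and overall response, and their agreement with the two-part definition that both documents describe. The endpoint is exploratory.

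**Working it through.** The documents give no expected responder rate or power for this endpoint, so there is no stated figure to reproduce.

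**1. Algebra.** Let B > 0 be baseline, F follow-up and d = F - B. The percent condition is d/B <= -0.20, so d <= -0.20 x B < 0. Every such d satisfies d <= 10. This holds on any scale and needs no distribution.

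**2. Enumeration of attainable scores.** Items run 0-10 (SAP 16.2). Pain has 5 items and function 17 (Protocol 7.3.2). Steps on 0-100 are 100/50 = 2 for pain, 100/170 = 0.59 for function and 10 for PGA. All baseline and follow-up pairs with a relative change of -20% or lower were counted, with all items answered. The -10 column is an assumption.

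| Domain | Pairs at <= -20% | Fail <= 10 | Fail <= -10 | Highest baseline affected by -10 |
|---|---|---|---|---|
| Pain, 0-100 | 1050 | 0 | 44 | 40.0 |
| Function, 0-100 | 11730 | 0 | 560 | 47.1 |
| PGA, 0-100 | 50 | 0 | 0 | none |
| PGA, raw 0-10 | 50 | 0 | 49 | 10 (only 10 to 0 passes) |

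These are counts of possible score pairs, not of subjects. If the item-level missing rule in SAP 16.2 applies here, all 4112 pain and 369648 function pairs still pass +10. The highest baselines affected by -10 become 47.5 and 49.4.

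**3. Direction.** Changes at or below a negative limit are a subset of those at or below +10. Per-domain, moderate and overall response under the printed rule are therefore equal or higher, never lower. The high-improvement rule is untouched.

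**4. Who is affected.** With a limit of -c, a subject is wrongly admitted in a domain if d <= -0.20 x B but d > -c. That requires 0.20 x B < c, so B < 5c. For c = 5, 10 and 15, this means baselines below 25, 50 and 75. Example at c = 10: pain 40 to 32 is a change of -8, or -8/40 = -20%. It counts as moderate improvement as printed, but not at -10.

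**5. Size at -10.** The documents give no distributions, so all of the following are assumed:
- baseline SD 18, mean change -12, SD of change 20;
- between-domain correlation 0.6, change independent of baseline;
- scores rounded to attainable steps and clipped to 0-100, with PGA on 0-100.

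Protocol 5.3.1 (criterion 8) and 5.4 require WOMAC Question 1 of 4 to 9, which thins out low baselines. Question 1 was modelled as the pain score plus noise of SD 8 or 15, and only subjects scoring 4 to 9 at baseline were kept.

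| Mean baseline before restriction | Excess in overall response, +10 minus -10 |
|---|---|
| 40 | 1.5 to 1.8 points |
| 50 | 0.8 to 1.0 points |
| 60 | 0.4 to 0.5 points |

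In the first row, the mean pain baseline among those kept is about 49 to 50. Only mean baseline and noise were varied under the restriction.

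**6. Arm comparison and 10% condition.** The same rule applies in every arm. The arm difference shifts by one non-negative excess minus another, so by no more than the larger of the two. The 10% condition would change only if overall response lay within that excess of 10%. In every case run, response was well above 10%.

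**The case against.** **The minus may only have been lost in reading the PDF.** The SAP text drops dashes elsewhere: in the knee-angle formula (13.3), the duration-of-exposure formula (15), the header of the SF-36 scoring table and the PGIC range (both 16.5). This stands as a reason to check the source before anything else. It does not dispose of the point. Three signed numbers survive in the same two bullets, and a signed number after an inequality survives in SAP section 10: "baseline mal-alignment in target knee (< -3 or > 3 or [-3,3] degrees". The lost dashes all stand between two terms. That pattern suggests a fault in the source but does not prove one.

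**The intention is recoverable.** SAP 16.5 cites published criteria (reference 9), the high-improvement rule is signed, and the separate 10-point WOMAC responder is a decrease. A careful programmer would probably notice a clause that does nothing. This is fair and lowers the risk. However, the value -10 is not printed in this definition, and reference 9 was not available to confirm it.

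**The PGA scale is a side issue.** Under the printed rule, the scale makes no difference. Because per-domain response and PGA change are to be summarised, 0-100 is also the natural reading of SAP 16.2. A reader might infer that the plan intends raw PGA and so nearly removes that domain. The documents do not say so. The scale matters only once the limit is negative, and one sentence settles it.

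**Conclusion.** The point holds, at minor severity. It is certain, given the printed text, that the absolute condition excludes nobody and that moderate improvement is percent-only, contrary to Protocol 8.3.4 and the opening of SAP 16.5. Whether the signed SAP carries the same text is not certain.

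The size is small. Against an inferred -10, with PGA on 0-100 and the assumed distributions restricted to Question 1 of 4 to 9, overall response is overstated by roughly 0.4 to 2 points. A different true limit would change that figure.

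A reader might infer that the rule biases sprifermin against placebo, opens the 10% condition improperly or touches the main result. The documents do not support this. The rule is identical in all arms, and the possible shift in an arm difference is bounded by the excess itself. The 10% condition would be affected only if response lay very close to 10%. The primary endpoint, sample size and significance level do not use this definition.

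**What to change.** 1. Check the sign in SAP 16.5 against the signed SAP and its reference 9.
2. If the minus is absent, print a signed negative limit. By analogy with -20 and the 10-point WOMAC responder in SAP 16.5, this would be an absolute change <= -10, subject to reference 9.
3. Apply the same rule to overall response, moderate improvement, the per-domain summaries and the 10% condition.
4. Add one sentence stating that PGA enters this rule on 0-100, like pain and function. On the raw 0-10 item, a limit of -10 would pass only 1 of the 50 qualifying pairs.

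The cost is one character and one sentence, plus a re-run of the responder derivation if it is already programmed.

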7.7.2 Medical Outcomes Study Short Form-36 General Health Survey

The MOS SF-36 (version 2.0) is a multi-purpose questionnaire that measures general health status and QOL, is not knee specific, and is the single PRO measure included to assess the overall status of the patient. It consists of 36 items that evaluate 8 dimensions of health: physical function, bodily pain, general mental health, vitality (energy and fatigue), social function, physical role (role limitations due to physical health), emotional role (role limitations due to

personal or emotional problems), and general health perceptions. Scores for the 8 dimensions/subscales range from 0 to 100, with higher scores representing better QOL. The MOS SF-36 is a generic measure as opposed to one targeting a specific age group, disease, or treatment. Accordingly, it has proven useful in surveys of general and specific populations, comparing the relative burden of different diseases, and examining the health benefits associated with a wide range of treatments. It should be noted that there is no defined MOS SF-36 score that represents a healthy, unimpaired condition. A subject with no disease symptoms would not necessarily have subscale scores of 100 or corresponding physical, mental, and summary scores of 400 or 800.

According to the User's Manual for the MOS SF-36 v. 2.0 Health Survey and Kosinski et al. (35), "minimal important differences" in MOS SF-36 scores consist of changes of 2 to 4 points, depending on the subscale concerned.

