Each scale is directly transformed into a 0-100 scale on the assumption that each question carries equal weight. All of the scales are scored so that the least health has a value of 0 and the greatest health has a value of 100.

Table 4 Scoring transformation for MOS SF-36

Sub score	# of items and range of scale	Total possible score	Items need to be reversed (max- item+1)	Normalizing Algorithm to 0-100= [(item[or average of items]min)/range]*100
GH	5 items with 1-5	5-25	Q1, Q11b, Q11d	100*(average-1)/4
PF	10 items with 1-3	10-30		100* (average-1)/2
RP	4 items with 1-5	4-20		100* (average-1)/4
BP	2 items with 1-6 and 1-5	2-11	Q7, Q8	100*{[(Q7-1)/5]+[(Q8-1)/4]}/2
VT	4 items with 1-5	4-20	Q9a, Q9e	100* (average-1)/4
SF	2 items with 1-5	2-10	Q6	100* (average-1)/4

RE	3 items with 1-5	3-15		100* (average-1)/4
МН	5 items with 1-5	5-25	Q9d, Q9h	100* (average-1)/4
Total	35 items	35-156	10 items	NA
Total score	36 items*	36-161	11 items **	100*{[sum of 10 items (item- 1)/2]+[sum of 25 items (item-
				1)/4]+[sum of 1 item (item- 1)/5]}/36

^{*}Q2 is only included in Total score (range of Q2: 1-5); **Q2 need to be reversed.

As long as at least 50% of the sub score items are answered for each sub score for a specific visit, a mean score can be imputed using the mean of the non-missing items for that visit. If more than 50% of the sub score items are omitted, the response is considered invalid and no sub score should be calculated. Similarly, same principle will be applied to Total score.

Sub scores and total score will be summarised by treatment and timepoint (including LOCF) along with the absolute change from baseline. Individual items as well as derived sub scores will be presented in listings.

The Numeric Rating Scale (NRS) for pain score

The NRS pain score in the target and contralateral knee is based on subject's answer to the question "Please indicate the worst pain in the past 24 hours in the target (contralateral) knee" and can take on values between 0-10 (0=No Pain, 10=Worst Pain imaginable).

The NRS will be presented with summary statistics by treatment and timepoint (including LOCF) as well as absolute change from baseline for target knee and contralateral separately. No imputation for missing data will be done. Individual items will be listed.

Pain in other joints

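### The SF-36 missing-item rule does not put items on a common range first, so Bodily Pain and Total can be mis-scored and can leave 0–100

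*SAP*

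**What the plan says.** The SF-36 part of SAP 16.5 gives scoring formulas in Table 4 and a missing-item rule below the table.

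- **Formulas.** Seven sub scores (GH, PF, RP, VT, SF, RE, MH) have items that share one range, and their formulas use the item average. Bodily Pain (BP) has "2 items with 1-6 and 1-5" and is scored as "100*{[(Q7-1)/5]+[(Q8-1)/4]}/2". Total sums 36 items, dividing 10 by 2, 25 by 4 and one by 5 after subtracting 1 from each, and then divides by 36.
- **Bounds.** "All of the scales are scored so that the least health has a value of 0 and the greatest health has a value of 100".
- **Missing items.** Provided that at least 50% of the items are answered, the rule is that "for each sub score for a specific visit, a mean score can be imputed using the mean of the non-missing items". The SAP then adds: "Similarly, same principle will be applied to Total score".
- **Reversal.** Table 4 lists the items to reverse, including Q7 and Q8. It does not say whether imputation comes before or after reversal.

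The KOOS part of the same section has an almost identical rule. There the SAP explains that the imputation amounts to the arithmetic mean of the answered items.

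**The concern.** A mean of item answers can stand in for a missing item only if all the items run over the same range. Every KOOS item runs 0–4, so the rule is safe there. BP and Total divide different items by different ranges, so a mean formed on one range enters a term that divides by another.

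BP has two items, so one answered item meets the 50% threshold and its value is used for the other. For Total, a missing 1–3 physical-function item receives a mean formed mostly from 1–5 items. The resulting score can be wrong, and it can fall outside the bounds the SAP sets.

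The MOS SF-36 is collected at baseline and at ten later visits (Protocol Appendix E). A mis-scored baseline enters every later change from baseline for that subject, and a mis-scored last visit enters the LOCF summary.

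**Working it through.** **Inputs.** Item ranges, formulas, reversals and the 50% threshold come from SAP 16.5, Table 4 and the text around it.

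**1. Complete data reproduce the plan.** The ranges give a BP raw maximum of 6 + 5 = 11. The 35 sub-score items give 10×3 + 24×5 + 6 = 156, and adding Q2 gives 161. All match Table 4. BP at best health is 100 × (5/5 + 4/4)/2 = 100. Total at best health is 100 × (10 + 25 + 1)/36 = 100. At worst health both are 0. The formulas are sound for complete questionnaires.

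**2. BP with one item answered, imputing after reversal.** Let k be the answered, reversed value. The other item also becomes k:

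100 × [(k-1)/5 + (k-1)/4]/2 = 22.5(k-1).

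Rescaling the answered item by its own range gives 20(k-1) from Q7 or 25(k-1) from Q8.

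| k | Plain reading | Own range, Q7 answered | Own range, Q8 answered |
|---|---|---|---|
| 1 | 0 | 0 | 0 |
| 2 | 22.5 | 20 | 25 |
| 3 | 45 | 40 | 50 |
| 4 | 67.5 | 60 | 75 |
| 5 | 90 | 80 | 100 |
| 6 | 112.5 | 100 | – |

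The error is +2.5 per step when only Q7 is answered (0 to +12.5) and -2.5 per step when only Q8 is answered (0 to -10). A pain-free subject scores 112.5 or 90 instead of 100.

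**3. BP with one item answered, imputing before reversal.** Let r be the unreversed answer. Reversal gives Q7 = 7-r and Q8 = 6-r, so

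100 × [(6-r)/5 + (5-r)/4]/2 = 122.5 - 22.5r.

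A pain-free subject (r = 1) now scores 100, which is correct. The error moves to the severe end. With only Q7 answered at its worst (r = 6), BP is 122.5 - 135 = -12.5 instead of 0. With only Q8 answered at its worst (r = 5), BP is 10 instead of 0.

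**4. Total, using reversed values.** Take a subject in best health on every answered item; the correct Total is 100.

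- One physical-function item missing: the mean of the other 35 is (9×3 + 25×5 + 6)/35 = 158/35 = 4.51. Total = 100 × [9 + 3.51/2 + 25 + 1]/36 = 102.1.
- All ten missing: the mean is (25×5 + 6)/26 = 131/26 = 5.04. Total = 100 × [10 × 4.04/2 + 25 + 1]/36 = 128.3.
- One 1–5 item missing: 99.6. Q7 missing: 99.1.
- Eighteen 1–5 items missing, the most the 50% threshold allows: 86.8.

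With one physical-function item missing, a subject at mid-scale throughout scores 51.1 instead of 50, and one at 75% of every range scores 76.6 instead of 75. At worst health the error is zero, because the imputed value is 1.

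**5. Rescaling first.** Averaging (item-1)/(own range) over the answered items gives the correct value in every case above and cannot leave 0–100.

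**The case against.** The best defence is that the SAP never calls the mean a raw one. Table 4's column heading normalizes at item level, the text gives each question equal weight, and the BP and Total formulas are themselves means of range-normalized items. A programmer who averaged the answered normalized items would get the right scores, and the 0–100 bound favours that reading. This stands as a possible reading. It is not written, and the KOOS sentence that the SF-36 rule echoes takes the mean over item answers.

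SAP 11 and Protocol 8.5.1 also defer to the questionnaire developers' rules for single missing items, and SAP 16.5 cites the SF-36 user's guide for the transformation. The guide is not among the documents, so whether it settles the matter cannot be checked. SAP 16.5 prints its own rule in any case.

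The consequence is also limited. SF-36 is exploratory (Protocol 8.3.4), is marked descriptive in SAP 19.1 and is absent from the key outputs in SAP 19.5. Individual items are listed, so a score above 100 or below 0 could be noticed and recomputed. An error that stays inside the bounds would be harder to see.

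Two stronger inferences should be resisted. A reader might conclude that every affected score moves by more than the important differences in Protocol 7.7.2, "changes of 2 to 4 points, depending on the subscale concerned". The figures do not support that: BP errors start at zero and the first step is 2.5, and one missing physical-function item moves Total by only about 1 to 2 points. That benchmark also concerns subscales, and Total is not one. A reader might also suppose that Total would be the answered items' sum divided by 36, giving 100 × 26/36 = 72.2 for the best-health subject with the physical-function block blank. That reading ignores the imputation sentence.

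**Conclusion.** The point holds as a minor correction. On the plain reading, the rule gives wrong BP and Total scores for some incomplete questionnaires and can breach the SAP's own bounds. The absolute error is 0 to 12.5 points on BP with one item answered. On Total it is about 1 to 2 points for one missing physical-function item in a subject between mid-scale and best health. The 128.3 figure is an extreme case.

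The sign depends on which item is missing. For BP it also depends on whether imputation precedes or follows reversal: 112.5 and 90 assume after, and -12.5 assumes before. The documents give no missing-item rate, so the effect on group means cannot be computed. The seven equal-range sub scores, complete questionnaires, and the primary, secondary and safety endpoints are untouched. The documents do not show that the scores will in fact be programmed wrongly; they show that the written rule permits it.

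**What to change.** In SAP 16.5 and Table 4, state that each answered item is first reversed where required and then rescaled to (item-1)/(its own range), and that BP and Total equal 100 times the mean of the answered rescaled items. Keep the existing 50% rule. No further condition on Total is needed, such as requiring all eight sub scores to be valid, because rescaling alone removes the problem.

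The cost is one sentence and a small programming change. With complete data the result equals the Table 4 formulas, so no complete-questionnaire score changes. The sentence also settles the order of reversal and imputation.
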